Procedure or Assessment	Screening (Day -30 to Day -1)	W1D1	W2D1	W3D1	W4D1	W5D1	W6D1	W7D1	Q3W (W10, W13, etc.)	End of Treatment (EOT) ^b	100-Day Follow-up (100DFU) ^c	Posttreatment Follow-up (PTFU) ^d (Q3mo)	Long-term Survival Follow-up (LTSFU) ^e (Q3mo)
Visit Windows	n/a	n/a	± 2d	± 2d	± 2d	±2d	±2d	±2d	± 3d	+7d	+7d	± 2 weeks	± 4 weeks
12-Lead ECG ¹	X	X		X				X		X			
Clinical Laboratory Tests (hematology, serum chemistry, urinalysis) ^m	X	X	X	X	X	X	X	X					
Coagulation Tests ^m	X	X						X	X	X			
Thyroid Function Tests ^m	X			X				X	X	X			
Pregnancy Test and Follicle Stimulating Hormone ^m	X	X			X			X	X	X			
Biomarkers													
Serum for Cytokine analysis ⁿ		X		X	X			X		X			
Serum for exploratory biomarkers (eg, anti-Qb Ab) ⁿ		X			X			X		X			
Plasma for ctDNA		X		X		X		X		X			
Archived tumor tissue ^p	X												
Blood DNA sample (germline control for mutational analysis) ^t	X												
Blood DNA sample for Pharmacogenomics (Optional) ^u	X												

Table 1: Schedule of Assessments (Continued)

Procedure or Assessment	Screening (Day -30 to Day -1)	W1D1	W2D1	W3D1	W4D1	W5D1	W6D1	W7D1	Q3W (W10, W13, etc.)	End of Treatment (EOT) ^b	100-Day Follow-up (100DFU) ^c	Posttreatment Follow-up (PTFU) ^d (Q3mo)	Long-term Survival Follow-up (LTSFU) ^e (Q3mo)
Visit Windows	n/a	n/a	± 2d	± 3d	± 7d	± 7d	± 2 weeks	± 4 weeks					
Fresh Tumor Biopsy ^o	X				X								
Disease Assessment (radiographic imaging) ^q	X ^r								W10 ^q ; Q9W	X ^q		X	
Disease Assessment (CNS Imaging) ^q	X ^r								W10 ^r ; Q9W	X ^q		X	
Disease Assessment (photographic imaging) ^q	X ^r	X							X	X ^q		X	
100-day Follow-up (Office or Phone Call)												X	
Long-Term Survival Follow-up Phone Call													X

Abbreviations: 100DFU = 100-Day Follow-up; ACTH = adrenocorticotrophic hormone; AE = adverse event; BMI = body mass index; CNS = central nervous system; d = day; CR = complete response; CRS = cytokine release syndrome; CT = computed tomography; ECG = electrocardiogram; ECOG = Eastern Cooperative Oncology Group; EOT = end of treatment; FSH = follicle-stimulating hormone; INR = international normalized ratio; IT = intratumorally; LTSFU = long-term survival follow-up; MRI = magnetic resonance imaging; n/a = not applicable; PD = progressive disease; PD-1 = programmed cell death protein 1; PD-L1 = programmed death-ligand 1; PE = physical examination; PR = partial response; PT = prothrombin time; PTFU = posttreatment follow-up; PTT = partial thromboplastin time; Q3W = every 3 weeks; Q3mo = every 3 months; Qb = Qbeta; QTc = QT corrected; RECIST = Response Evaluation Criteria in Solid Tumors; SC = subcutaneously; W = week; WOCBP = women of childbearing potential.

a. The W4D2 visit is mandatory but may be waived under certain circumstances. The site must contact the medical monitor for a waiver. (Note: Footnote "a" is not applicable from Protocol Amendment 5)

b. End of Treatment assessments are to be performed within 30 days (±7 days) after subject discontinuation from last study treatment. Subjects who discontinue vidutolimod but continue on treatment with cemiplimab will have separate EOT visits for both vidutolimod and cemiplimab. Removal of a subject from vidutolimod treatment is defined as the time in which the Investigator decides to discontinue study treatment. If a subject has vidutolimod dosing withheld for more than 3 consecutive doses for any reason during the Q3W dosing period, resumption of treatment must be discussed with the Medical Monitor; otherwise, the subject will be discontinued from study treatment and will have all EOT assessments performed.

- c. AEs and concomitant medications data will be collected until 100 days (± 7 days) after the last dose of study drug (vidutolimod or cemiplimab) or until an alternative anticancer treatment is initiated, or until overall End of Clinical Trial (Section 3.4), whichever occurs first. The 100DFU should occur 100 days (± 7 days) from the last study treatment (vidutolimod or cemiplimab) and may be conducted at the study site or via phone.
- d. Posttreatment follow-up (PTFU) will be conducted Q3mo (± 2 weeks) for all subjects who discontinue study treatment but have not met criteria for study discontinuation. These subjects should remain on study and receive disease assessments Q3mo, until disease progression or discontinuation of PTFU for any reason. For an individual subject, the maximum duration of PTFU is 18 months. After completing PTFU, subjects go to LTSFU.
- e. LTSFU will be conducted Q3mo (± 4 weeks) after the EOT visit or the last disease assessment date in PTFU and may occur via phone. LTSFU may continue until overall End of Clinical Trial (Section 3.4).
- f. Vidutolimod dosing will begin on W1D1. A window of ± 2 days is permitted for vidutolimod weekly dosing from W1D1 to W7D1. The first dose of vidutolimod may be administered SC or IT, at the discretion of the Investigator; all subsequent doses are planned to be administered IT until no injectable lesions remain. Subjects must complete all 7 weekly vidutolimod doses before moving to the Q3W dosing schedule. Q3W dosing (W10D1+): A window of ± 3 days is permitted for vidutolimod dosing from W10D1 throughout the study. When cemiplimab treatment is permanently discontinued, vidutolimod must also be permanently discontinued. Refer to Section 4.3 for treatment compliance.
- g. Treatment with cemiplimab will begin on W1D1 and continue Q3W throughout the study. When vidutolimod injection and cemiplimab dosing fall on the same day, vidutolimod injection will be given before cemiplimab. Refer to Section 4.1.2 for details of cemiplimab dosing.
- h. A full PE will be conducted at Screening and EOT. If the Screening full PE is performed >72 hours before the W1D1 visit, then a brief (symptom directed) PE must be performed within 72 hours before the first injection of vidutolimod. Brief PEs focused on areas of disease or AEs must be performed at every vidutolimod injection visit (before vidutolimod administration), and at any other time as clinically indicated. Height will be obtained at Screening only and weight at all PE assessments.
- i. Vital signs include measurement of blood pressure (systolic and diastolic blood pressure), respiratory rate, heart rate, and body temperature. Blood pressure and heart rate should be taken in the seated position following ≥ 3 minutes of rest. For the first 6 vidutolimod dosing visits (W1D1 to W6D1), vital signs must be collected prior to the vidutolimod injection (± 10 minutes) and at 30-minute (± 15 minutes) intervals for 4 hours after vidutolimod injection. Starting at W7D1, observation periods may be reduced to a minimum of 1 hour following vidutolimod injection at the Investigator's discretion based on the AE profile of the individual subject. When vital signs are scheduled at the same time as collection of a blood sample, the vital sign measurements should be obtained before the scheduled phlebotomy. If a study visit occurs where only cemiplimab is administered, vital signs must be collected before the start of cemiplimab infusion.

NOTE: Oxygen saturation is not a required parameter to be collected. Sites are to capture oxygen saturation every time an AE of hypoxia or CRS is reported for a subject.

- j. AEs will be assessed from time of consent through 100 days after the last dose of study treatment or until an alternative anticancer treatment is initiated, whichever occurs first. Subjects who discontinue vidutolimod but remain on treatment with cemiplimab will continue to have AEs collected according to this schedule until 100 days after the last dose of cemiplimab or until an alternative anticancer treatment is initiated, whichever occurs first. Any SAEs related to IP will continue to be assessed.
- k. Concomitant medications will be assessed continually from 30 days before the first dose of study treatment through 100 days after the last dose of study treatment or until an alternative anticancer treatment is initiated, whichever occurs first. Treatment medications for study-related AEs that occur through 100 days after the last dose of study treatment will be collected during the 100DFU period.
- l. 12-lead ECGs will be obtained at Screening, before the W1D1, W3D1, and W7D1 vidutolimod injections, and at EOT. ECG parameters will include heart rate and PR interval, QRS, QT, and QTc intervals. ECGs will be performed after the subject has been resting in supine or semi-supine position for at least 5 minutes. When an ECG is scheduled at the same time as a blood sampling, the ECG reading should be obtained before the scheduled blood sampling.
- m. Clinical laboratory assessments may be performed up to 72 hours before vidutolimod injection. When clinical laboratory assessments are done the same day as vidutolimod injection, vital signs should be performed prior to collection of clinical laboratory tests. Refer to Section 6.1.12 for Clinical Laboratory Assessments.

Note: For WOCBP, a serum pregnancy test and FSH are completed at Screening and W1D1. WOCBP must have a negative serum or urine pregnancy test (minimum sensitivity 25 IU/L or equivalent units of human chorionic gonadotropin) within 24 hours prior to the start of study treatment. An extension up to 72 hours prior to the start of study treatment is permissible in situations where results cannot be obtained within the standard 24-hour window. Serum or urine pregnancy tests are also to be completed prior to vidutolimod injection on W4D1, W7D1, and Q3W thereafter and EOT. Refer to Section 6.1.13 for pregnancy testing. An additional pregnancy test must be conducted at the end of the relevant systemic exposure, ie, 16-18 weeks after last study dose treatment. A urine test conducted at home and communicated to the investigator by phone would be acceptable. Pregnancy testing should be performed in women having a bilateral tubal ligation. A follicle stimulating hormone test is required to confirm menopause in women with less than 12 months of amenorrhea. If fertility is unclear and a menstrual cycle cannot be confirmed before the first dose of study treatment (W1D1), subject should be considered of childbearing potential and applicable pregnancy tests completed.

Note: Coagulation samples (PT, INR, and PTT) are to be collected prior to the W1D1 visit. Subsequent results are to be reviewed before every vidutolimod injection beginning at W7D1 and continuing Q3W thereafter.

Note: At Screening, subjects assessed as at risk for adrenal insufficiency should undergo diagnostic tests for ACTH and morning cortisol, and/or high-dose ACTH stimulation test (preferred testing method), if clinically indicated, via local laboratory.

n. Serum samples are to be collected at the following time points:

- Within 2 hours before vidutolimod injection on W1D1, W3D1, W4D1, W7D1
- 4 hours (\pm 30 minutes) after the start time of the vidutolimod injection on W1D1, W4D1, W7D1
- 2 hours (\pm 30 minutes) after the start time of the vidutolimod injection on W3D1

Refer to Section 6.3.1. Collection of Blood for Translational Biomarker Analyses.

o. Fresh tumor biopsy samples are mandatory, if safe and medically feasible, at Screening (before W1D1) and at W4D1 3 to 4 hours after vidutolimod IT injection. If the Investigator believes it is unsafe to perform a biopsy, the subject may be considered eligible after discussion with the Medical Monitor. Refer to Section 6.3.2 for tumor biopsies.

p. Archival tumor biopsy samples should be collected during Screening, if available. If archived FFPE slides (instead of archived block) are provided, the slides must be \leq 5 months old after being cut from the tissue block.

q. Disease Assessment methods include radiographic (contrast-enhanced CT or MRI), photographic, and CNS imaging by contrast enhanced CT or MRI (per site local standards). The same modality used at Screening must be used throughout the study. Disease assessments will be performed at screening and predose beginning at W10D1 (-7 days) and repeated every 9 weeks (-7 days) (eg, W19D1, W28D1, etc). Digital photographs of visible vidutolimod injected and noninjected skin lesions should be taken at baseline and if a clinically relevant change occurs. Disease assessments will continue every 9 weeks after the confirmatory scans. All scans should be performed at least 2 weeks after the previous vidutolimod IT injection to prevent injection-related pseudoprogression. Disease assessments may be performed every 12 weeks for subjects with a response continuing more than 1 year. Refer to Section 6.2 for disease assessments. NOTE: Imaging at the EOT visit is not required if the subject has had imaging within 60 days of the visit according to the modality by which the subject's disease was being monitored (CT, MRI, and/or photography) or if the subject has had disease progression. Imaging to confirm progression is encouraged but not mandatory.

r. Baseline brain imaging by contrast-enhanced CT or MRI (per site local standards, brain MRI preferred) should be provided at Screening for subjects with known or suspected brain metastases. On-study brain imaging is only required for subjects with current or prior history of brain metastases or clinical signs or symptoms of CNS disease. Photographic and/or radiographic images demonstrating disease progression on prior PD-1-blocking antibody treatment will be collected whenever available.

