6.6. Posttreatment Follow-Up

Subjects who discontinue study treatment and transition into PTFU will continue to have assessments collected per the time points specified in the Schedule of Assessments ([Table 1](#)). Posttreatment follow-up disease assessments will continue until disease progression, initiation of another cancer treatment, death, lost to follow-up (at least 3 documented attempts to contact the subject), withdrawal of consent, End of Clinical Trial, or maximum of 18 months- in PTFU for an individual subject.

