## 7. EFFICACY DATA

### 7.1. Description of Efficacy Data

All endpoints below will be assessed based on data reported by the investigators.

ORR is defined as the number of patients with a best overall response (BOR) of confirmed complete response (CR) or partial response (PR) divided by the total number of patients.

- Confirmation of CR or PR must occur during a subsequent evaluation at a timepoint of at least 4 weeks from the initial assessment of CR or PR.
- Best overall response of SD must have met the response SD criteria at least once  $\geq 56$  days (9 weeks for first tumor assessment –7 days window) from the first study treatment administration
- Patient(s) without baseline tumor assessment or with either unknown or missing BOR will be counted as non-responder(s).

DOR, defined as time from first confirmed response of CR or PR to first radiographic progression or death due to any cause for patients with confirmed CR or PR. In the absence of radiographic progression or death on or before the analysis cutoff date or the date of initiation of a further anti-cancer treatment, the DOR will be censored at the date of the last valid response assessment not showing progression performed on or prior to the analysis cutoff date or initiation of a further anti-cancer treatment, whichever is earlier.

DCR, defined as the percentage of patients with a BOR of CR, PR, or stable disease (SD).

TTR, defined as time from first study treatment administration to first confirmed response of CR or PR for patients with confirmed CR or PR.

PFS defined as time from the first study treatment administration to first radiographic progression or death due to any cause. The same censoring rule as DOR will be used.

OS defined as the time from first study treatment administration to death due to any cause. For patients who have not died, OS will be censored at the last date that patient is known to be alive.

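### The 60-day waiver of end-of-treatment imaging has no exception for an unconfirmed CR or PR, so a subject who stops both drugs after one response scan can go about 3 to 5 months before a scan that could confirm it

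*Protocol*

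**What the plan says.** **Confirmation.** The primary endpoint is confirmed ORR (Protocol 2.2.1 and 8.6.1). SAP 7.1 states: "Confirmation of CR or PR must occur during a subsequent evaluation at a timepoint of at least 4 weeks", counted from the initial response. It sets no maximum interval.

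**On treatment.** Protocol 3.1 schedules scans at W10D1 and every 9 weeks after that while treatment continues. Footnote q of Table 1 adds: "Disease assessments will continue every 9 weeks after the confirmatory scans". No visit in Table 1 is designated as a confirmatory scan, so the next 9-weekly scan serves as one.

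**End of treatment (EOT).** Footnote b reads "End of Treatment assessments are to be performed within 30 days", with a window of 7 days either side, counted from discontinuation. Footnote q then says: "Imaging at the EOT visit is not required if the subject has had imaging within 60 days of the visit". It does not mention a pending response.

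**After treatment.** Subjects who stop for reasons other than progression enter posttreatment follow-up (PTFU; Protocol 3.2). Footnote d says: "These subjects should remain on study and receive disease assessments Q3mo, until disease progression or discontinuation of PTFU for any reason". The window is 2 weeks either side, and no start date for the 3 months is given. Under Protocol 6.6, "Posttreatment follow-up disease assessments will continue until disease progression, initiation of another cancer treatment" or one of several other events, including death, loss to follow-up and withdrawal of consent.

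**The concern.** An EOT scan can confirm a response first seen at least 28 days before it. The waiver applies whenever the last scan is no more than 60 days old. A response first seen 28 to 60 days before EOT is therefore one that an EOT scan could confirm, yet it falls within the waiver. No other passage restores the scan. Protocol 6.2.2 asks for continued confirmation photographs after a CR, but it refers back to Table 1.

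The next scheduled chance is the first PTFU scan. If progression, another cancer treatment, death or dropout comes first, the subject is counted as a non-responder, even if the response was still present 4 to 9 weeks after it was first seen. The loss would come from the scan calendar and would fall on subjects who stop early without progression, for example for an adverse event.

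**Working it through.** **1. The plan's own figures.** The documents give no figure for the scan gap. The only numerical targets on the primary endpoint are in Protocol Table 12 (SAP Table 1). With n = 25, the exact two-sided 90% lower bound for x responders is the 5% quantile of Beta(x, 26 − x). This reproduces every listed bound. The last column shows the effect of one lost confirmation (1/25 = 4 points).

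| Cohorts | Threshold | Lower bound | Listed | One response fewer |
|---|---|---|---|---|
| A1, B1, D | 18/25 (72%) | 53.8% | >50% | 17/25: 49.6% |
| A2, B2, C2 | 6/25 (24%) | 11.0% | >10% | 5/25: 8.2% |
| C1, F | 10/25 (40%) | 23.6% | >21% | 9/25: 20.2% |
| E | 15/25 (60%) | 41.7% | >39% | 14/25: 37.9% |

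For F, 20.2% is below the listed 21% but still above the 19% reference rate.

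**2. Gap between scans.** Inputs are the 60-day waiver (footnote q), the 3-month interval with its 14-day window (footnote d), and 3 months taken as 91 days.

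- 3 months counted from the last scan: 91 days, or 91 + 14 = 105 at the late end of the window.
- 3 months counted from EOT, with a scan 60 days before EOT: 60 + 91 = 151 days, or 151 + 14 = 165 at the late end.
- On treatment, for comparison: 9 × 7 = 63 days.

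**3. Can it happen?** Take a first PR at W10D1 (day 64), last dose at W13D1 (day 85), and EOT 30 days later (day 115).

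- Scan to EOT: 115 − 64 = 51 days, or 58 if the scan was taken 7 days early. Both are inside 60, so the EOT scan may be omitted.
- Next scan if counted from EOT: day 115 + 91 = 206 (192 to 220 with the window), which is 142 days after the first PR.
- Next scan if counted from the last scan: day 64 + 91 = 155.
- The 9-weekly calendar would have scanned at W19D1, day 127. The delay is therefore 79 days (206 − 127) or 28 days (155 − 127).

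With the last dose at W10D1, EOT falls nominally 30 days after the scan. The gap counted from EOT is then 30 + 91 = 121 days.

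**4. Illustration of how often a wait costs a response.** Assume exponential duration of response. The share progressed by time t is 1 − exp(−ln 2 × t / median), with a month taken as 30.44 days. Protocol 1.3.1.3 gives a median of 19.9 months (95% CI 6 to 19.9) in an earlier melanoma study. The 12-month row is an assumed intermediate value.

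| Median | 28 days | 60 days | 105 days | 151 days |
|---|---|---|---|---|
| 19.9 months | 3% | 7% | 11% | 16% |
| 12 months | 5% | 11% | 18% | 25% |
| 6 months | 10% | 20% | 33% | 44% |

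These shares cover progression only. They apply only to subjects who stop with a single unconfirmed response, and the documents do not say how many that would be.

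**The case against.** The strongest reply is that the exposed group is narrow and the long gap is not the usual case. Most of this stands.

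- **The EOT date can move.** Footnote b ties removal from vidutolimod to the investigator's decision. If, in the example, that decision came at W16D1 (day 106), EOT at day 136 would be 72 days after the scan (65 to 79 with the window). The scan would then be required and could confirm. The waiver applies in some sequences, not all.
- **Many subjects stay on the 9-weekly calendar.** Imaging continues through dosing delays (Protocol 3.1 and 4.1.2.1), and subjects who stop only vidutolimod remain on treatment. Elective stopping for CR already requires confirmation (Protocol 3.2).
- **The waiver permits omission and does not forbid a scan.** SAP 11.4 allows unscheduled measurements to be used. That is true, but it leaves confirmation of the primary endpoint to site discretion.
- **The step across a Table 12 bound is not special to this issue.** Any one subject matters at the threshold. SAP 1.2 states no formal hypothesis, and ORR is reported with a 95% interval. The table shows sensitivity; it is not a decision rule that would fail.

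A reader might infer that every such subject waits 5 months. The documents do not support that: it is the worst case and assumes PTFU is counted from EOT, which is nowhere stated. A reader might also infer that the response will be lost. It need not be, because the SAP sets no latest time for confirmation. Nor does the point extend to PFS and DOR. Coarser imaging after treatment is an ordinary trade-off for descriptive secondary endpoints.

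**Conclusion.** The gap in the rules is real, and its likely effect is small. For a subject who stops both drugs without progression after one CR or PR, with EOT 28 to 60 days after that scan, the plan makes optional the scan that could confirm the response. The next scheduled scan comes about 3 to 5 months after the first response scan, depending on an unstated start point and on when EOT falls. A response is lost only if progression, new therapy, death or dropout comes first.

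The bias in confirmed ORR is downward, so it cannot create false evidence of activity. Each lost response costs 4 points in a cohort of 25. The total effect cannot be estimated, because the number of exposed subjects is not given; it is probably small. The shares in the illustration rest on an assumed exponential duration and, for the 6- and 19.9-month rows, on figures from a different tumor type. The case for a change is that it is specific and cheap, not that a cohort's conclusion is in danger.

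**What to change.** In footnote q and Protocol 6.6:

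1. State that the 60-day waiver does not apply to a subject with a CR or PR not yet confirmed.
2. For that subject, obtain one scan at least 4 weeks after the first response scan and, where feasible, before new anticancer treatment starts. Take it at EOT, or shortly after EOT if EOT falls before the 4 weeks are up; otherwise the scan would come too early to confirm.
3. State the date from which the 3-monthly PTFU assessments are counted.

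For the exposed subjects, the interval from the first response scan to one that can confirm it falls to roughly 28 to 60 days.

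Do not move every PTFU subject's first scan onto the 9-weekly calendar. That would add imaging burden for all who enter PTFU to solve a problem confined to a few.

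The cost is amendment wording and one scan, already in the schedule, kept or slightly shifted in the few subjects who stop with an unconfirmed response. Only the timing of measurement changes.
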